9.6 Data Management and Storage Process

9.6.1 Data Management

Data management and data quality check will be performed to remove errors and inconsistencies in order to assure the appropriateness of the study data set to assess the study objectives. Data entry screens will be developed and tested prior to initiating data collection to reduce data entry errors. If required, IMS will provide AbbVie with data for analysis.

Each site coordinator will be instructed to answer patients' queries which may arise in relation to the questionnaires and check the patients' input to make sure all questions are answered.

9.6.2 Storage Process

Following data quality checks, each dataset will be converted to SAS and merged for analysis. All information included in the CRF and the patients' questionnaires will be checked in order to detect possible queries to solve and will be extracted to a specifically designed database, where it will be validated by IMS personnel to ensure its quality. Finally, data analysis will be conducted and final results reported.

The databases will be stored in IMS data servers. Data servers are submitted to daily backups in order to increase the security on all data managed in the collection process.

All paper based questionnaires will be stored in a secured, locked area for a period of seven (7) years, after which all data will be shred using an agency specialized in disposal of confidential documents.

9.7 Data Analysis

9.7.1 Statistical and Analytic plans

A statistical analysis plan (SAP) will be developed describing the specific analysis that will be performed including, and in addition to, the analysis described here. All analysis will be performed in accordance with the approved analysis plan. The following provides an overview of some of the analysis.

The scoring of the PRO questionnaires will be done in accordance to the developers' recommendations.

A separate statistical analysis plan will be developed describing the specific analysis that will be performed including and in addition to the analysis described here.

9.7.2 Analyzable population

All subjects who received at least one dose of adalimumab during the study will be included. The main analysis will be conducted on the pooled population, where appropriate, with each individual country analyzed separately as supportive data.

9.7.3 Planned Methods of Statistical Analysis

All statistical tests will be two-tailed with a significance level of 0.05. Descriptive statistics will be provided. Descriptive analysis will be conducted on all key parameters and presented as mean, standard deviation, minimum, maximum, and median when continuous and as "n" and percent when categorical. Change from adalimumab initiation to 24 weeks will be calculated and evaluated for significant improvements using paired t-tests / ANOVA for parametric and Wilcoxon signed-rank for non-parametric data. Analysis will be also be conducted by severity level (moderate vs severe), disease duration quartile (to compare to prior work) and up to two (2) other subgroups. Cochran-Armitage test of trends or other similar methods may be used to compare categories of subjects.

9.7.4 Primary Endpoint Analysis

The primary endpoint variable will be the change in HAQ DI score at week 24 after the initiation of adalimumab, in those patients continuing on adalimumab.

The objective of the primary endpoint analysis will be to demonstrate that treatment with adalimumab improves functioning as measured by the HAQ DI in subjects with RA following treatment initiation. This change will be summarized as the mean and 95% confidence interval and will be tested with a paired t-test.

The primary analysis will be summarized as the mean and 95% confidence interval and will be tested with a paired t-test without adjusting for baseline disease severity. For sensitivity analysis, the mean change in HAQ DI at week 24 will be analyzed using ANOVA adjusting for baseline disease severity.

9.7.5 Secondary Endpoint Analysis

The main secondary endpoint variable will be the change in HAQ DI at week 12 after the initiation of adalimumab.

The objective of endpoint analysis will be to demonstrate that treatment with adalimumab improves functioning as measured by HAQ DI in subjects with RA compared to baseline.

The main secondary analysis will be summarized as the mean and 95% confidence interval and will be tested with a paired t-test without adjusting for baseline disease severity. For sensitivity analysis, the mean change in HAQ DI at week 12 will be analyzed using ANOVA adjusting for baseline disease severity.

Other secondary analysis include:

- Change in other patient reported outcomes (SF-36 domain scales, EQ-5D Index, WPAI total lost productivity) at weeks 12 and 24 after the initiation of adalimumab, in those patients continuing on adalimumab. These changes will be summarized as the means and 95% confidence intervals and will be tested with paired t-tests.
- Number and percent of patients achieving a clinically meaningful improvement on the HAQ DI, as defined by a -0.22 point improvement or greater, at weeks 12 and 24 after the initiation of adalimumab, in those patients continuing on adalimumab.

9.7.6 Additional Secondary Endpoint Analysis

Additional efficacy analysis include:

- Change in HAQ DI score at 24 weeks after the initiation of adalimumab, in those patients continuing on adalimumab, compared with those patients not continuing on adalimumab. The mean changes in these two groups will be compared using an independent t-test.
- Healthcare resource utilization will be described using number and percentage within each category (number of consultations, number of procedures received, number of surgeries, number of hospitalizations and length of stay, number of concomitant medications)
- Associations between disease severity and PROs
- Associations between change in disease severity and change in PROs

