9.5 Study Size

Approximately 52 patients diagnosed with RA will be recruited. The planned sample size provides 80% power for detecting a statistically significant improvement in HAQ-DI (Δ HAQ-DI < 0) assuming a mean Δ HAQ-DI of -0.21 and a standard deviation of 0.5 (reference 11), at two-sided significance level of 0.05 and accounting for a 10% dropout rate. The sample size also provides 99% power for detecting a statistically significant clinically meaningful improvement in HAQ-DI (Δ HAQ-DI < -0.22) assuming a mean Δ HAQ-DI of -0.5 and a standard deviation of 0.7, at two-sided significance level of 0.05 and accounting for a 10% dropout rate.

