9.7.10 Missing Data

Efficacy measures are not assessed after a participant discontinues adalimumab. The exception to this will be the analysis of proportion of patients at 24 weeks who remain on adalimumab. Item level data on the PROs will be imputed according to the developers’ recommendations. There will be no other imputation for missing data.

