### 5.3 Analysis Plan for Primary Objectives

The objective of the primary endpoint analysis will be to demonstrate that treatment with adalimumab improves functioning as measured by the HAQ DI score in subjects with RA following treatment initiation (i.e. baseline).

- The changes in HAQ DI score at 12 and 24 weeks after the initiation of adalimumab will be presented (Excel Table 3.1); these changes will be summarized as the mean, SD, minimum, maximum, median, Q1, Q3; as well as the number and percent of patients achieving a clinically meaningful improvement on the HAQ DI, as defined by a -0.22 point improvement or greater. In addition, the mean or median change will be tested with a paired t-test or paired Wilcoxon signed-rank test without adjusting for baseline disease severity; for sensitivity analysis, the mean change will be analyzed using ANCOVA adjusting for baseline disease severity.
- The change in HAQ DI score at 24 weeks after the initiation of adalimumab (mean, SD, minimum, maximum, median, Q1, Q3), in those patients continuing on adalimumab (observed population) will be compared with those patients not continuing on adalimumab (withdrawal population). The mean or median changes in these two groups will be compared using an independent t-test or paired Wilcoxon signed-rank test listed in the table (Excel Table 3.2).

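### The t-test of week-24 HAQ DI change in patients continuing versus not continuing adalimumab is presented as an efficacy analysis, but its groups form after baseline and may depend on response, so a difference cannot be read as a drug effect.

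*Protocol*

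**What the plan says.** Protocol 9.7.6 opens its list with "Additional efficacy analysis include". The first item is the change in HAQ DI at 24 weeks in patients continuing adalimumab against those not continuing, and "The mean changes in these two groups will be compared using an independent t-test". Protocol 4.0 and 9.1 plan the same test among the additional secondary endpoints. Protocol 9.7.3 sets the level: "All statistical tests will be two-tailed with a significance level of 0.05".

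The SAP is divided on its status. Section 2.3 lists it as exploratory. Section 5.3 plans it (Table 3.2) as the second item under the primary objectives, in a section that opens: "The objective of the primary endpoint analysis will be to demonstrate that treatment with adalimumab improves functioning as measured by the HAQ DI score".

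The groups are defined in the note closing Protocol 9.1: a patient who misses two injections in a row, or three in total that are not consecutive, within the 24 weeks counts as not continuing. Patients may stop at any time (9.1), and being switched off the drug counts as drop-out (12.6). On follow-up, Protocol 9.7.10 says "Efficacy measures are not assessed after a participant discontinues adalimumab", while Table 1 schedules a HAQ at early termination.

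**The concern.** Continuation is not assigned. It is observed during the same 24 weeks over which the outcome develops. If patients whose function does not improve are more likely to miss injections, stop or be switched, the outcome helps to form the groups. Continuers will then show the better mean change whether or not adalimumab works.

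Neither document offers an adjustment, a landmark or a caution for this comparison. Protocol 9.9 mentions only limited and missing data. SAP 3.5.5 says that missing data cannot be taken as missing completely at random or at random. That sits badly with treating stopping as unrelated to outcome, which is the condition under which this test would keep its 5% level as a test of efficacy.

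The placement matters because the primary analysis is an uncontrolled before-after test. A significant between-group p-value for HAQ DI, reported with the efficacy results, could be taken for controlled evidence of benefit by the payers for whom the study is partly intended (Protocol 7.0, SAP 1.1).

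**Working it through.** **The plan's own figure.** Protocol 9.5 states "Approximately 52 patients diagnosed with RA will be recruited" and "The planned sample size provides 80% power for detecting a statistically significant improvement in HAQ-DI", "assuming a mean Δ HAQ-DI of -0.21 and a standard deviation of 0.5", at two-sided 0.05 with 10% dropout. This is for the paired primary test.

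- Normal approximation: (1.960 + 0.842)² × (0.5/0.21)² = 7.85 × 5.67 = 44.5, so 45 patients.
- Exact noncentral t: 47 patients, power 80.5%; 47/0.9 = 52.2.

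The planned 52 therefore reproduces, to rounding. Neither document states a size or power for the comparison at issue.

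**Inputs for the check.** N = 52, SD of change 0.5 and two-sided 0.05 come from the protocol. The true mean change is set to 0 (no drug effect). The share not continuing is taken as 10%, about 5 of 52. That is an assumption: the protocol's 10% is a dropout allowance, not a non-continuation rate. The strength of the link between response and stopping is also an assumption, because the documents give none.

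**Model 1.** Early change e ~ N(0,1), positive meaning worse. Recorded change = 0.5 × (ρe + √(1−ρ²) × noise). The log-odds of stopping are linear in e, with slope ln(OR) and an intercept that gives 10% stopping. The test is a pooled two-sample t-test.

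| Odds ratio of stopping per SD of worse early change | Correlation ρ of early and recorded change | Rejection rate |
|---|---|---|
| 1 (no link) | any | 5% |
| 1.25–1.5 | 0.6–1.0 | about 6–14% |
| 2 | 0.6–1.0 | about 14–30% |
| 3 | 0.6–1.0 | about 24–58% |
| 2 and 3 | 0.3 | about 7% and 9% |

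With 30% stopping, for which the documents give no source, the rates at ρ 0.6–1.0 are 24–57% (OR 2) and 43–87% (OR 3). Across the OR 2–3 runs at both shares and ρ 0.6–1.0, the spurious difference is about −0.19 to −0.49 HAQ units, nearly always favouring continuers.

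**Model 2.** A latent tendency to stop is correlated r with worse change, and the 5 patients with the highest tendency stop. Rejection is 7%, 12%, 22%, 37% and 55% at r = 0.1, 0.2, 0.3, 0.4 and 0.5. If 7 of 52 stop (the SAP's 13%), it is 7%, 14%, 26%, 44% and 65%.

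A hand check at r = 0.3:

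- The expected gap is r × SD × φ(1.282)/(0.1 × 0.9) = 0.3 × 0.5 × 0.1755/0.09 = 0.29 (simulated 0.28).
- The standard error is 0.5 × √(1/5 + 1/47) = 0.235.
- The ratio is 0.28/0.235 = 1.2 against a critical value of 2.01, so the rejection probability is about Φ(1.2 − 2.01) = 0.21. This agrees with the simulated 22%.

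That gap of 0.28 exceeds the 0.21 for which the study is powered.

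**Model 3.** Only patients short of −0.22 at week 12 stop, 15% of them. Since P(change > −0.22) = Φ(0.44) = 0.67, about 10% stop overall. With week-12/week-24 correlation 0.5–0.7, rejection is 8–12% if week-24 values are used for those who stop, and 17–18% if the value at stopping is used.

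**The case against.** Four points on the other side have force.

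1. **The link is not documented.** A reader might infer that the test rejects far above 5% in any case. The documents do not support that. Protocol 7.0 says patients pay for the drug, and SAP 1.1 cites high cost and a 3-month average duration of use. Stopping for cost, or for other reasons unrelated to function, would bring the rate back towards 5%.

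2. **The t-test is correct for its literal null.** That null is equal mean change in the two groups. If non-improvers stop, the means do differ and rejection is right. The error arises only when the result is read as evidence of efficacy.

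3. **The labels are loose.** The list in Protocol 9.7.6 also covers resource use and severity–PRO associations. The aim quoted from SAP 5.3 concerns the primary endpoint analysis, and SAP 2.3 words the comparison as description. This lowers the stakes but does not remove the ambiguity: the test still sits under an efficacy label in one document and under the primary objective in the other.

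4. **Not continuing is not the same as leaving the study.** A reader might infer that the comparison holds no follow-up after stopping. The definition by missed injections allows a patient to stay in the study and complete a week-24 HAQ. What can be said is narrower: Protocol 9.7.10, Table 1 and the Protocol 9.1 note leave it unclear which HAQ value represents this group.

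Nor does the point reach the primary result, which does not use this comparison.

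**Conclusion.** The concern holds in a conditional form. The groups are formed after baseline, response may influence membership, and nothing in the plan separates the two. A difference between continuers and non-continuers therefore cannot be interpreted as an effect of adalimumab. That conclusion needs no simulation.

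The size of the problem depends on an unknown. With no drug effect, 52 patients, SD 0.5 and 10% not continuing, the rejection rate is 5% with no link, about 6–14% with a weak link (OR 1.25–1.5 per SD) and about 14–58% with a moderate to strong link (OR 2–3). Both linked ranges take correlations of 0.6–1.0; a lower correlation gives less, and a larger share stopping gives more. The other two models fall in the same broad range. The plan should be changed because it invites the efficacy reading, not because a particular error rate is established.

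**What to change.** - **Protocol 4.0, 9.1 and 9.7.6; SAP 2.3 and 5.3 (Table 3.2):** delete the between-group test and its p-value. This also disposes of the SAP's fallback for this item, a paired Wilcoxon test, which does not suit two separate groups.
- **Protocol 9.7.6:** take the comparison out from under the efficacy label.
- **SAP:** move the item from 5.3 to 5.5, in line with its exploratory status in 2.3.
- **Reporting:** for each group give n, mean HAQ DI change, 95% CI and the timing of the HAQ used.
- **Interpretation:** state that the difference reflects who stays on treatment and does not estimate adalimumab's effect.
- **Reasons for stopping:** list them only if the study already records them. Table 1 shows no such item.

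The cost is wording in two documents and one revised table, with no new data. One secondary p-value is lost. The interval for non-continuers will be wide: with 5 patients and SD 0.5, about ±2.776 × 0.5/√5 = ±0.62. That is an honest picture of how little this group can show.

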9.7.7 Exploratory Endpoint Analysis

- Change in patient satisfaction questions at weeks 12 and 24 after the initiation of adalimumab, in those patients continuing on adalimumab. These changes will be summarized as number and percentage of each response and compared with Kruskal–Wallis test. Satisfaction will also be dichotomized and analyzed over time with Cochran-Armitage test for trends.
- Patient’s impression of change at weeks 12 and 24 after the initiation of adalimumab, in those patients continuing on adalimumab (as observed population). These changes will be summarized as number and percentage of each response and compared with Kruskal–Wallis test.

9.7.8 Safety Analysis

Adverse events occurring while participants are on adalimumab will be coded using Common Terminology Criteria for Adverse Events (CTCAE) classification individually listed by indication groups. The incidences and percentages of individuals experiencing AEs and SAEs within each indication will be summarized by System Organ Class (SOC) with further summaries by severity and relatedness (causality) categories. Adverse events leading to discontinuation and concomitant medications will also be listed and summarized.

9.7.9 Additional Analysis

Additional analysis will explore the potential modifying effects of baseline measures on the changes in primary and secondary efficacy outcomes. These measures will include age, gender, baseline severity, and other diagnoses/co-morbidities. The analysis will specifically test for differential changes across the subgroups defined by the potential modifiers using general linear models.

9.7.10 Missing Data

Efficacy measures are not assessed after a participant discontinues adalimumab. The exception to this will be the analysis of proportion of patients at 24 weeks who remain on adalimumab. Item level data on the PROs will be imputed according to the developers’ recommendations. There will be no other imputation for missing data.

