9.9 Limitations of the Research Methods

The study is to be performed as a non-interventional study. Unlike clinical studies, obtainable data are limited and there is a possibility of missing data.

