### 2.1 Primary Objectives

- To describe the change in HAQ DI score at 24 weeks after the initiation of adalimumab (i.e. baseline), in those patients continuing on adalimumab (as observed population). This change will be summarized as the mean and 95% confidence interval or median (Q1,Q3) and will be tested with

a paired t-test or paired Wilcoxon signed-rank test without adjusting for baseline disease severity. For sensitivity analysis, the mean change in HAQ DI at Week 24 will be analyzed using ANCOVA adjusting for baseline disease severity.

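### No planned HAQ DI estimate covers all treated patients: the week-24 change and the −0.22 responder rate count only those who stay on adalimumab

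*Protocol*

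**What the plan says.** Protocol 9.7.4 defines the primary endpoint as the week-24 HAQ DI change in patients who stay on treatment. Its aim is to "demonstrate that treatment with adalimumab improves functioning as measured by the HAQ DI in subjects with RA following treatment initiation". The responder endpoint in Protocol 9.7.5 requires a "0.22 point improvement or greater, at weeks 12 and 24 after the initiation of adalimumab, in those patients continuing on adalimumab". SAP 2.1 keeps the restriction for the primary objective ("in those patients continuing on adalimumab (as observed population"), and SAP 2.2 keeps it for the responder count.

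One sensitivity analysis is planned. Protocol 9.7.4: "For sensitivity analysis, the mean change in HAQ DI at week 24 will be analyzed using ANOVA adjusting for baseline disease severity". SAP 5.3: "for sensitivity analysis, the mean change will be analyzed using ANCOVA adjusting for baseline disease severity".

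Protocol 9.7.2 describes a wider set: "All subjects who received at least one dose of adalimumab during the study will be included". No HAQ DI analysis is assigned to it.

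On missing data, Protocol 9.7.10 says "Efficacy measures are not assessed after a participant discontinues adalimumab", and SAP 3.5.5 repeats this. Both name one exception, the share still taking adalimumab at 24 weeks. Both allow outcome imputation only for questionnaire items. Protocol 9.9 says that "obtainable data are limited and there is a possibility of missing data" and does not mention selection on staying on treatment.

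Protocol 9.7.6 and SAP 2.3 and 5.3 also compare the week-24 change between patients who continue and patients who do not.

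**The concern.** The aim is worded for RA patients who start adalimumab, but the estimate describes those who stay on it. Patients who stop may do so because they are not improving. If so, both the mean change and the responder rate look better than they are for everyone treated. If patients stop for unrelated reasons, there may be little difference. The plan as written cannot show which.

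Stopping is foreseeable here. SAP 1.1 gives an average duration of use in China of only 3 months, against a 24-week endpoint. The stated readers include payers and officials deciding on insurance coverage, who would want to know the result in everyone treated.

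**Working it through.** **1. Which patients each HAQ DI analysis covers**

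| Analysis | Place | Patients |
|---|---|---|
| Week-24 mean change | Protocol 9.7.4, SAP 2.1 | Continuing only |
| −0.22 responders | Protocol 9.7.5, SAP 2.2 | Continuing only |
| Severity-adjusted sensitivity | Protocol 9.7.4, SAP 2.1 and 5.3 | Same patients |
| Continuing versus not | Protocol 9.7.6, SAP 2.3 and 5.3 | Two groups, no pooled estimate |

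The first bullet of SAP 5.3 (Table 3.1) omits the restriction. Read with Protocol 9.7.2, it could be taken to mean all treated patients. However, SAP 2.1 and 2.2, which it implements, impose the restriction. Even without it, patients not assessed after stopping and not imputed would have no week-24 value. This is a conflict to resolve and does not amount to an all-treated estimate.

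**2. The plan's own figure.** Protocol 9.5 assumes a mean of −0.21, SD 0.5, two-sided alpha 0.05 and 10% dropout. The standardized change is 0.21/0.5 = 0.42. A paired t-test (noncentral t) needs 47 evaluable patients, with power 80.5%. 47/0.90 = 52.2 and 47 × 1.10 = 51.7, so the planned 52 reproduces. The calculation treats dropout only as fewer patients, not as a possible difference in outcome.

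**3. Shift in the mean.** Let p be the share outside the continuing group and M_s their mean change:

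M_all = (1 − p) × (−0.21) + p × M_s

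| p | M_s = 0 | M_s = −0.105 (half) | M_s = +0.10 (worse) | M_s = −0.21 (equal) |
|---|---|---|---|---|
| 0.10 (Protocol 9.5) | −0.189 | −0.1995 | −0.179 | −0.21 |
| 0.13 (SAP 4) | −0.1827 | −0.1964 | −0.1697 | −0.21 |
| 0.30 (assumed) | −0.147 | −0.1785 | −0.117 | −0.21 |

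For example, 0.90 × (−0.21) + 0.10 × 0 = −0.189, a shift of 0.021. At 30% the shift is 0.21 − 0.147 = 0.063. All values of M_s are assumptions; the documents give none.

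**4. Responder rate.** If the change is taken as normal with the Protocol 9.5 mean and SD, the on-treatment rate is Φ((−0.22 + 0.21)/0.5) = Φ(−0.02) = 49.2%. If nobody outside the continuing group has a week-24 HAQ, the all-treated rate lies between 0.492 × (1 − p), with all of them non-responders, and that value plus p, with all of them responders:

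- p = 0.10: 44.3% to 54.3%
- p = 0.30: 34.4% to 64.4%

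**5. Whether the planned comparison fills the gap.** The relevant texts are:

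- Protocol 9.7.6 asks for a 24-week change in non-continuers.
- Protocol 9.7.10 and SAP 3.5.5 say efficacy is not assessed after stopping.
- Protocol 12.6 makes switching off adalimumab a study drop-out.
- Protocol Table 1 schedules a HAQ at early termination. Protocol 9.1 accepts a visit as week 24 only within ±7 days.
- The note in Protocol 9.1 defines non-continuing by missed injections. Such a patient may remain in the study and have a true week-24 HAQ.
- The SAP calls the group the withdrawal population and does not carry that note over.

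One analyst could use only non-continuers with a week-24 HAQ, and another could use early-termination values. Even with a usable HAQ for every non-continuer, a true difference of 0.21 with SD 0.5 gives power of about 14% (47 versus 5), 22% (42 versus 10) or 28% (36 versus 16). A non-significant result would not reassure.

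**The case against.** The restriction is declared in the endpoint and labelled as observed, so nothing is hidden. The plan also holds information on patients who stop: the share still on drug, the comparison, counts of missing data (SAP 3.5.5) and adverse events leading to discontinuation (Protocol 9.7.8). This stands. It means the primary analysis can remain, but none of these items yields an all-treated HAQ DI estimate.

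Some stronger readings are tempting and are not supported:

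- A reader might infer that nothing planned covers all treated patients. The share still on adalimumab does. What is missing is a table for it in SAP 6.
- A reader might infer that non-continuing has two rival definitions. The Protocol 9.1 note defines it; Protocol 12.6 defines study drop-out, a different thing.
- A reader might infer that no rule governs an early-termination HAQ. The ±7-day window and the bar on imputation together imply that one outside the window is not a week-24 value. What remains is the conflict between a week-24 comparison in non-continuers and the statement that they are not assessed after stopping.
- A reader might want the sentence in SAP 3.5.5 on data not missing at random removed. It does not justify available-case analysis for all treated patients, but it admits that missingness may be informative. Deleting it would change no result.

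An obvious remedy, using the early-termination or week-12 HAQ in place of week 24, also has a cost. It is last observation carried forward and assumes that benefit persists after stopping.

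**Conclusion.** The point holds as a gap in supporting analyses that should be filled. The week-24 HAQ DI results describe patients who stay on adalimumab, and no planned HAQ DI estimate describes everyone treated. The direction depends on stoppers improving less, which the documents neither show nor exclude.

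The size is uncertain. At the plan's 10% dropout with no change in stoppers, the shift of 0.021 is about a tenth of the 0.22 threshold. At an assumed 30% it is 0.063. It is zero if stoppers change as much as continuers.

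A reader might infer from the 3-month average use that about half the sample will stop before week 24. The documents do not support that. The figure is general background and not a stopping rate for this study, and Protocol 9.2.2 (exclusion 4) and SAP 3.2.2 exclude patients whom the clinician doubts can adhere for 24 weeks. Nor would an all-treated estimate isolate the drug's effect, since the study has no comparator. It addresses only the selection on staying on treatment, under stated assumptions for patients without a week-24 value.

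**What to change.** Keep the primary analysis unchanged, and mark the additions with the date on which they were made.

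- **Responder rate.** Report the week-24 rate with all treated patients (Protocol 9.7.2) as denominator. Count those without a week-24 HAQ first as non-responders and then as responders.
- **Mean change.** Add a sensitivity analysis in all treated patients, using any week-24 HAQ whatever the treatment status. For the others, vary the week-24 change over a stated range that includes return to baseline, some worsening and the continuers' mean. If early-termination or week-12 values are also used, name this as last observation carried forward, state its persistence assumption, report the source and timing of each value, and amend the no-imputation wording in Protocol 9.7.10 and SAP 3.5.5 for this analysis.
- **Share on treatment.** Add a table of the share still on adalimumab at week 24 to SAP 6.
- **Comparison.** Reconcile Protocol 9.1 (note and visit window), Table 1, 9.7.6, 9.7.10 and 12.6 with SAP 2.3, 3.5.5 and 5.3. The group should be the one in the Protocol 9.1 note, and its HAQ visit should be stated. Align the first bullet of SAP 5.3 with SAP 2.1 and 2.2.

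The cost is a few table rows and some wording, with no visits beyond those in Table 1. The downside is that results for patients without a week-24 HAQ rest on untestable assumptions, which is why they are shown as a range.
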